5.2.4. Interval Sample Size Reassessment

We defined length of treatment for the proposed trial as the average number of days of opioid treatment from the first weaning dose to cessation of opioid treatment. Due to a lack of available studies with published parameter estimates, we based the standard deviation used in the power calculations (6.9 to 8.0 days) on the number of days of opioid treatment for the *entire* interval of drug treatment, from initiation to cessation of morphine or methadone treatment (18). We anticipate that a

smaller standard deviation may be present in the proposed trial since we are only studying weaning. To address the concerns that the standard deviation may be lower than 6.9 days for our primary outcome, we will perform an interval sample size reassessment.

The interval sample size reassessment will occur after 25% of the enrolled infants are medically ready for discharge, which will be 126 infants, assuming full enrollment of 502 infants. This coincides with the first Data Monitoring and Safety Committee (DSMC) safety review (see **Section 5.5.2**). The NRN DCC will re-estimate the sample size and provide the DSMC with this report. To re-estimate the sample size, we will use the pooled variance estimate calculated across both intervention groups from blinded data observed in 126 study participants. This blinded look at the interim data used for sample size refinement will not require any alpha adjustment in the final primary outcome analysis.

5.3. AVAILABLE POPULATION

In the fall of 2017, a ISPCTN and NRN site survey found that during a one-year period, there were approximately 2,700 infants exposed to opioids, of which, medical professionals pharmacologically treated approximately 43%. Among those treated pharmacologically, medical professionals treated 76% with morphine, 24% with methadone, and 4% with buprenorphine. These observations provide a starting point to estimate the number of participants available for this trial. However, there is some uncertainty regarding how many NOWS infants would meet the inclusion criteria without meeting any exclusion criteria (Exclusion Criteria, Section 1). In addition, there may be changes in hospital practices within the ISPCTN and NRN given ongoing NOWS initiatives. Multiple clinical trials have not achieved enrollment of the projected sample size (15, 17, and 18), and we expect low consent rates in this population. Use of the Recruitment Plan (**Appendix 3**) was associated with a 35% consent rate at Women and Infants Hospital for the methadone vs morphine trial conducted by Davis et al (18) in contrast to 26% among all participating centers. **Table 7** provides an estimate of the number of infants enrolled per year based on estimates of available infants ranging from 1,250 to 750 and consent rates ranging from 20% to 30%. Twenty hospitals in the NRN and ISPCTN have expressed interest in participation in this clinical trial.

Table 7. Estimated Enrollment per Year

Consent Rate	Enrollment by Consent Rate and Infant Numbers		
	1,250 available infants	1,000 available infants	750 available infants
20%	250	200	150
25%	313	250	188
30%	375	300	225

5.4. PROJECTED RECRUITMENT TIME

Based on the estimates of the available population and a target enrollment of 502 infants, a conservative estimate to complete the trial would be 3.3 years (750 infants available for the trial each year and a consent rate of 20%). This translates to an average monthly enrollment requirement of 12-13 infants. If enrollment is slower than projected, we may consider other hospitals through the National Center for Advancing Translational Science and the National Institutes of Drug Abuse Clinical and Translational Science Awards.

5.4.1. Assessment of Enrollment Target

The study subcommittee will review subject accrual at two years after 100% of participating hospitals have been IRB approved and are screening infants for enrollment. This review will permit a more precise determination of attainable sample size with continued enrollment into the trial. The projected sample size and recruitment duration requires an enrollment of 12-13 infants each month. Variables that we could evaluate, other than meeting the projected enrollment rate, include an increasing enrollment rate between year one and two, and/or enrollment of >75% of the target. In addition, if the monthly recruitment into the trial at this point, based on a three-month moving average, falls below 5, the DSMC will be asked to conduct a review of study feasibility. This review may include ad hoc safety, efficacy and futility analyses that will allow the DSMC to make a recommendation regarding trial termination or continuation to the leadership of the participating Networks and NIH.

Meeting Recruitment Targets. Infants with NOWS are a challenging patient group to study given parental concerns about social or legal ramifications of enrolling their infants in trials, as seen in randomized trials that have been unable to enroll the projected sample size (15, 17, and 18). The approach to the care and management of opioid addiction during pregnancy and the newborn has shown a growing appreciation that care should be multidisciplinary, collaborative, non-judgmental, and centered on the mother-infant pair (2). To minimize the number of hospitals with slow recruitment, we will provide participating hospitals the following framework.

- Prior to the initiation of screening, each hospital will provide a hospital specific recruitment plan, the expected number of available patients and a proposed schema to identify patients (before and after birth), including a plan for tracking to ensure eligibility and establishing points of contact(s) with the mother.
- Once screening has been ongoing for six months, the Data Coordinating Centers (DCCs) of both networks will review screening logs, the number of eligible infants, consent rates, and reasons for eligible but not consented infants.
- We will conduct conference calls with hospitals that are not meeting recruitment metrics. The calls will involve the DCCs, trial Principal Investigators and NIH personnel. The purpose of these calls is to ensure that hospitals have examined their process and identified changes in their approach to improve recruitment. The DCCs will offer successful recruitment practices from other hospitals.

5.5. STUDY MONITORING PLAN

5.5.1. Reporting Adverse Events

Study personnel will report all AEs (**Section 4.2.12**) and SAEs (**Section 4.2.13**) on the appropriate form and enter the data into the electronic data capture system (EDC). Refer to **Section 4.2.12** for a listing of the adverse events.

Study personnel will promptly report (within 24 hours of knowledge) all SAEs that the study intervention at least possibly relates to or are unexpected to the study sponsor and the DCC. The designated Medical Monitor will review these events and will forward them to the Chair of the DSMC. Study personnel must complete an initial SAE form, including details of the current SAE, and provide an Investigator

assessment of the causal relationship between the event and study procedures. Study personnel must document information not available at the time of the initial report on a follow-up SAE form.

5.5.2. Data Monitoring Plan and Stopping Rules

There is wide variability in weaning opioid drug treatment across IDeA States and NRR hospitals. Well-characterized AEs and a DSMC will be critical to monitor the trial and to assure that the interventions are safe. The DSMC will assess safety after 25%, 50%, and 75% of the enrolled infants are medically ready for discharge, and it will assess efficacy and futility after 50% of the enrolled infants are medically ready for discharge. All interim analyses will utilize Bayesian modeling and predictive posterior inference based on neutral, enthusiastic, and skeptical priors. We will use Bayesian modeling for the interim analyses because the predictive posterior inference makes a clear statement about what to expect when we complete frequentist analysis on final data, given the interim results. The DSMC will receive an independent presentation of interim results, prepared by the study statistician. In preparation for the DSMC meeting, we will prepare a summary report of recruitment (by hospital), known outcome events, and any AEs (including medication side effects).

Interim Futility and Efficacy Analysis. For interim efficacy, we will use Bayesian posterior predictive probabilities to predict the final outcome of the trial based on interim results. For this predictive probability calculation, we will use a frequentist criterion: reject null hypothesis if final analysis p-value is less than or equal to 0.05. Given this criterion and the neutral, enthusiastic, and skeptical priors defined above, we will calculate three predictive probabilities of success (PPoS) when 50% of the total sample is collected by using the three reference priors: neutral, skeptical, and enthusiastic. To calculate a PPoS, we will take the following steps:

4. Choose the neutral, enthusiastic, or skeptical prior for the treatment effect.
5. Fit a Bayesian linear regression model to the primary outcome using the interim data. Include maternal treatment and stabilization dose as covariates.
6. Calculate the posterior distributions for all regression terms.
7. Use the interim data to calculate the observed distribution of maternal treatment.
8. Use the interim data to calculate the observed distribution of the stabilization dose. May approximate with a normal distribution if suitable.
9. Determine how many infants we still need to randomize in each arm.
10. For each arm, generate data for the required number of hypothetical participants by doing the following for each required hypothetical participants:
 - Sample a single value from each posterior distribution.
 - Make a random draw from the observed distribution for maternal treatment.
 - Make a random draw from the observed or approximated distribution for stabilization dose.
 - Use the appropriate sampled values from steps 7a – 7c to generate a hypothetical outcome.
11. Use the data observed plus the hypothetical data generated in Step 7, above, to create a hypothetical complete trial and calculate the p-value under the null hypothesis of $\theta = 0$. Use a linear regression model that includes treatment, maternal treatment, and stabilization dose.

12. Repeat Steps 7 and 8 many times. The PPoS is the proportion of hypothetical completed trials that achieve a p-value for the treatment effect that is 0.05 or less.²

The PPoS will be a helpful measure for the DSMC to use as it makes decisions about stopping the trial early for efficacy or futility or continuing to enroll. Below are two suggested guidelines for using the PPoS, but as stated in the DSMC charter, all protocol suggested stopping guidelines are advisory and the DSMC can choose to ignore them. If the PPoS is 0.99 or greater under the skeptical prior, then the DSMC may consider stopping the trial for efficacy. If the frequentist PPoS is 0.1 or less under the enthusiastic prior, then the DSMC may consider stopping the trial for futility. The PPoS under the neutral prior will also be available to aid interpretation of the PPoS estimates calculated under the skeptical and enthusiastic priors.

Interim Safety Analysis. In addition to monitoring AEs and SAEs, as described in section 5.5.1 above, the DSMC will use Bayesian analyses to monitor seizure occurrence. The DSMC will assess seizure occurrence at three interim reviews, 25%, 50%, and 75% of enrollment. Within the slow-wean intervention, we expect the seizure proportion to be 0.03, and within the rapid-wean intervention, we expect this proportion to be higher. Based on clinical experience, the study team offers the following guideline for stopping the trial early for safety. Yet as with Efficacy and Futility, per the DSMC charter, all protocol suggested stopping guidelines are advisory and the DSMC can choose to ignore them. If the seizure proportion is 0.03 in the slow-wean intervention, and the seizure proportion is greater than 0.10 in the rapid-wean intervention, then the DSMC may consider stopping the trial for safety. As such, the interim analyses of safety will focus on reporting information about the seizure proportion in the slow-wean intervention and the difference between seizure proportions in both interventions. At each interim analysis of safety, we will calculate the posterior distribution of seizure proportion within each intervention by using a simple Bayesian logistic regression model, intercept and treatment effect parameters with neutral priors on the intercept and the intervention effect parameter. We will place a normal ($\mu=0$, $\sigma=10$) on the intercept, and we will place a normal ($\mu=0$, $\sigma=3$) on the intervention effect term. Let θ_1 = proportion of infants with seizures in the rapid-wean intervention and θ_2 = proportion of infants with seizures in the rapid-wean intervention minus the proportion of infants with seizures in the slow-wean intervention. We will calculate the posterior distribution of θ_1 and θ_2 by using transformations of the MCMC values that make up the estimated posterior distributions for the intercept and the intervention effect parameter. If $\Pr(\theta_1 > 0.1 \mid \text{Data}) \geq 0.95$, and $\Pr(\theta_2 > 0.07 \mid \text{Data}) \geq 0.95$, then the DSMC may want to consider stopping the trial for safety.

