5.1. STATISTICAL ANALYSIS PLAN

5.1.1. Primary Hypothesis

Among infants receiving an opioid (defined as morphine or methadone) as the primary treatment for neonatal opioid withdrawal syndrome (NOWS), a rapid-wean intervention will reduce the days of opioid treatment from the first weaning dose to cessation of opioid compared to a slow-wean intervention.

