5.1.4. Analysis of the Primary Hypothesis and Outcome

We will determine the outcome of the primary hypothesis on an intention to treat basis. We will assign infants who exit the intervention at 35 days of methadone/morphine treatment either as 35 days of opioid treatment or we will treat them as a censored value at 35 days. We will determine intervention differences of two means by analyzing the average number of days of opioid treatment from the first

weaning dose to cessation of opioid treatment. We will analyze the data using regression models that will include the intervention as a fixed effect and will include maternal treatment and stabilization dose as covariates. We will include site (hospital) in the model as a random effect. The primary test of interest will be the F-test of the intervention effect, and we will report the intervention difference along with 95% confidence interval (CI).

Because of possible censoring and removal of participants due to intervention failure, we will conduct sensitivity analysis of the primary outcome using several methods. The first sensitivity analysis will replicate the analysis, described above, and include other covariates in the model that were significantly different across the two weaning intervention groups. Sensitivity analyses will also be conducted to evaluate the effects of infants who were and were not part of the Eat Sleep Console trial as a covariate or effect modifier (see **Section 5.2.2**). Another possible sensitivity analysis will include non-parametric and/or survival regression (e.g., negative binomial, median regression, or survival analyses), as there is potential for skewness and censoring in the primary outcome.

Finally, sensitivity analysis will include fitting a competing risks model to the data where the possible competing risk states are weaned, parental withdrawal, physician withdrawal, and treatment failure (unable to wean by 35 days of methadone/morphine treatment). We will fit Cox proportional hazards models to the data to estimate the intervention effect and other covariate effects on “cause-specific hazards.” The analysis of the “cause-specific hazards” will allow for additional inquiry into the intervention effect on the primary outcome while accounting for competing safety and withdrawal risks.

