 μ_i = expected value of outcome y_i

 β_0 = intercept, the expected mean number of treatment days when all covariates = 0

 β_1 = Intervention effect of fast vs slow wean interventions

 $\beta_2, \beta_3, \beta_4$ = effect of maternal treatment, compare to no treatment

 β_5 = effect of stabilization dose

 β_5 = effect of breastfeeding

 β_i = effect of the jth covariate added to the model

For normal outcomes, g(.) is the identity link function.

For binary outcomes, g(.) is the logit link function and we will assume that y_i follows Bernoulli distribution. Alternatively, we can follow Zou et al. (2003) and use the natural log function, and we will assume that y_i follows Poisson or negative binomial distribution. Decision will be based on manuscript writing team, if they prefer to report risks vs odd ratios.

For count outcomes, g(.) is the natural log function, and we will assume that y_i either follows Poisson or negative binomial distribution.

All hypothesis tests will be performed using a two-sided significance level of 0.05. Unless otherwise specified, results for each type regression performed will include the following:

- Normal regression
 - Unadjusted
 - Mean (and 95% confidence intervals (CI)) of the outcome in each treatment group.
 - Mean difference (and 95% CI) of the outcome between treatment groups.
 - Adjusted using pre-specified covariates.
 - Mean (and 95% CI) of the outcome in each treatment group.
 - Mean difference (and 95% CI and p-value) of the outcome between treatment groups.
- Logit Binomial regression
 - Unadjusted
 - Rate (and 95% CI) of the outcome in each treatment group
 - Odds Ratios (and 95% CI) of the outcome between treatment groups
 - Adjusted using pre-specified covariates.
 - Rate (and 95% CI) of the outcome in each treatment group
 - Odds Ratios (and 95% CI and p-value) of the outcome between treatment groups.
- Log-Binomial or Poisson regression
 - Unadjusted
 - Risk (and 95% CI) of the outcome in each treatment group
 - Relative risk (and 95% CI and p-value) of the outcome between treatment groups
 - Adjusted using pre-specified covariates.
 - Risk (and 95% CI) of the outcome in each treatment group
 - Relative risk (and 95% CI and p-value) of the outcome between treatment groups.
- Poisson or negative binomial regression
 - Unadjusted
 - Rate (and 95% CI) of the outcome in each treatment group
 - Relative rate (and 95% CI and p-value) of the outcome between treatment groups

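### The interim predictive-probability steps in protocol 5.5.2 redraw the parameters for each hypothetical infant and count significance in either direction, so both stopping guidelines trigger at the wrong interim results

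*Protocol*

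**What the plan says.** Protocol 5.5.2 plans an efficacy and futility assessment once half the enrolled infants are medically ready for discharge. A Bayesian model is fitted to the interim data, the remaining infants are simulated, and the completed trial is tested.

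- **Level of the simulation:** "For each arm, generate data for the required number of hypothetical participants by doing the following for each required hypothetical participants". The first action in that list is "Sample a single value from each posterior distribution". The outer repeat regenerates the data and the p-value and adds no parameter draw for the trial as a whole.
- **Success:** the criterion is "reject null hypothesis if final analysis p-value is less than or equal to 0.05", and "The PPoS is the proportion of hypothetical completed trials that achieve a p-value for the treatment effect that is 0.05 or less". Neither the definition nor the two guidelines mention direction. SAP 6.4.1 adds "All hypothesis tests will be performed using a two-sided significance level of 0.05".
- **Hypothesis (protocol 5.1.1):** "a rapid-wean intervention will reduce the days of opioid treatment from the first weaning dose to cessation of opioid compared to a slow-wean intervention".
- **Simulated final model:** "Use a linear regression model that includes treatment, maternal treatment, and stabilization dose". For the primary analysis, protocol 5.1.4 says "We will include site (hospital) in the model as a random effect".
- **Guidelines:** the DSMC may consider stopping for efficacy if PPoS is at least 0.99 under the skeptical prior, and for futility if it is at most 0.1 under the enthusiastic prior. Both are advisory.

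**The concern.** The treatment effect is unknown, but it is the same unknown value for every infant still to be randomized. A valid predictive simulation therefore draws it once per simulated trial. If each infant gets a fresh draw, the errors cancel over about 125 infants per arm, and the simulated second half behaves almost as if the effect were known to equal its posterior mean. PPoS is then pushed towards 0 or 1, most visibly near the 0.99 and 0.10 cut-offs.

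Separately, a two-sided p-value with no sign condition counts a trial in which rapid weaning significantly lengthens treatment as a success. A DSMC reading PPoS at face value would then have a rule that does not answer the trial's directional question.

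**Working it through.** **Inputs.** Difference 2.0 days, SD 6.9, 251 per arm (protocol 1.8). Skeptical prior mean +2, enthusiastic prior mean -2, both with SD 3 (protocol 5.1.6). Look at 50%, cut-offs 0.99 and 0.1 (protocol 5.5.2). Re-estimated SD 6.2 and target 302 (SAP 3.4). Write d for the interim difference, rapid minus slow; negative is benefit.

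**1. The plan's own figures.** Per arm, 2 × 6.9² × (1.960 + 1.282)² / 2² = 250.1, so 251, as stated. With SD 6.2 the same formula gives 404 in total for 90% power and 302 for 80%, also as stated. The documents give no PPoS value to reproduce.

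**2. Standard errors.** With 125.5 per arm at the look, SE = 6.9 × √(2/125.5) = 0.871. At the end, SE = 6.9 × √(2/251) = 0.616, so significance needs an absolute final difference above 1.96 × 0.616 = 1.207.

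**3. Posterior at the look.** Weight on the data = 9 / (9 + 0.871²) = 0.922. Posterior mean = 0.922 d + 0.078 × prior mean. Posterior variance = 0.700.

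**4. What the second half must show.** The halves are equal, so the final difference is (d + d₂)/2. Significant benefit needs d₂ < -2.414 - d. Significant harm needs d₂ > 2.414 - d.

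**5. Predictive SD of d₂.**
- One draw per simulated trial: √(0.700 + 0.759) = 1.208.
- One draw per infant, with intercept variance 6.9²/125.5 = 0.379: √[(2 × 47.61 + 2 × 0.379 + 0.700)/125.5] = 0.878, about 27% too small.

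**6. Worked points.**
- Skeptical prior, d = -2.5: posterior mean -2.150, cut-off 0.086. One draw per trial: (0.086 + 2.150)/1.208 = 1.85, PPoS 0.968. As written: 2.236/0.878 = 2.55, PPoS 0.995. Only the second crosses 0.99.
- Enthusiastic prior, d = -0.5: PPoS 0.143 with one draw per trial and 0.070 as written. Only the second crosses 0.10.
- Skeptical prior, d = +2 (harm): posterior mean 2.0, cut-off 0.414. As written: 1.586/0.878 = 1.81, PPoS 0.965. With one draw per trial but still no sign condition it is 0.905, and with a sign condition 0.000. The sign problem does not depend on how the loop is read.

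**7. Solving for the boundaries.**

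| | 502, SD 6.9: as written | 502: corrected | 302, SD 6.2: as written | 302: corrected |
|---|---|---|---|---|
| Efficacy met by benefit | d ≤ -2.40 | d ≤ -2.80 | d ≤ -2.83 | d ≤ -3.28 |
| Efficacy met by harm | d ≥ +2.24 | never | d ≥ +2.62 | never |
| Futility met | -0.59 to +0.75 | d ≥ -0.37 | -0.68 to +0.89 | d ≥ -0.43 |
| Futility if truth is -2 days | 5.2% | 3.1% | 9.3% | 6.0% |

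The harm-side efficacy trigger is nearer zero than the benefit-side one because the skeptical prior is centred on harm. If the truth is +2 days (N = 502), the efficacy guideline is met 39% of the time as written. The futility guideline is then met 7.4% of the time as written and 99.7% when corrected.

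**8. Check.** A Monte Carlo run with individual outcomes and a final t-test (4,000 completions per point, N = 502, SD 6.9) agreed with the closed form to within about 0.03. Drawing parameters jointly or separately within each infant made almost no difference.

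**9. Models side by side.** The simulated test has treatment, maternal treatment and stabilization dose, without hospital. Protocol 5.1.4 has those terms plus a random hospital effect. The SAP primary model (4.1, 6.5.1) has intervention plus random site only, and SAP 6.4.5 moves the covariates to a sensitivity analysis. The simulated test therefore matches neither document. The size of this mismatch was not calculated.

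**The case against.** The strongest reply is that the rule is no longer in play. SAP 3.7 says the interim will not be performed, SAP 3.6 reports no interim analysis after August 5, 2022, and SAP 3.4 says the trial was to end after December 31, 2023. That largely stands. Two gaps remain. SAP 3.6 says the DSMC will not look at primary outcome data a further time before study end, which leaves open whether an earlier look used this calculation. Protocol 5.4.1 also allows ad hoc efficacy and futility analyses, without saying how they would be computed.

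The steps may be a compressed summary of a standard method, with one draw per trial intended. That is possible, but the text places the draw inside the per-infant step.

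In a two-sided comparison of two schedules already in use, a likely significant result for slow weaning is arguably not futile. A DSMC that sees the estimate would hardly mistake a 2-day excess for efficacy. Both points are fair. They mean the rule should state what success means; they do not make a sign-free definition an efficacy rule.

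Three stronger readings are tempting and unsupported:
- A reader might infer that no harmful trend can meet the futility guideline. As written, trends up to about +0.75 days do meet it.
- A reader might count the rise in early efficacy stopping at a true effect of -2 days (18% to 32%) as error. Stopping for a real effect is not an error. With no effect, the benefit-side guideline is met 0.29% of the time as written against 0.07%.
- A reader might infer that a faulty PPoS steered the trial. The documents do not show that any PPoS was computed.

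**Conclusion.** Followed literally, the stopping calculation in protocol 5.5.2 gives wrong values. At 502 infants and SD 6.9, the efficacy boundary moves by about 0.4 days and the start of the futility region by about 0.22 days. Wrongful futility at the design effect is about 5% instead of 3%. The missing sign lets an excess of about 2.2 days or more meet the efficacy guideline and lets excesses above about 0.75 days escape the futility guideline. The pattern is the same at 302 infants and SD 6.2. Around PPoS 0.5 to 0.7 the effect of the redrawing is small.

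The figures assume equal arms, a known SD, residual error in each simulated outcome, and no covariates or hospital effect. Practical impact is limited to any look at or before the August 2022 review and any ad hoc review under 5.4.1. The final analysis is unaffected.

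**What to change.** 1. In protocol 5.5.2, take one joint sample of all parameters from the posterior for each simulated trial, and use it for every remaining infant in that trial.
2. Define success as a final p-value of 0.05 or less and an estimate favouring rapid wean. If the DSMC also wants the probability of a significant result favouring slow wean, report it separately.
3. Make the interim model and the simulated final model equal to the primary model actually used. In the SAP that is intervention plus random site. Adding hospital to match protocol 5.1.4 would still predict a different analysis, so reconcile the two documents first.
4. State whether any PPoS was computed at or before the August 2022 DSMC review and how. If one was, recompute it.
5. If the rule will not be used again, withdraw it from the current protocol instead of rewriting it.

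The cost is a few lines of protocol text and simulation code, and somewhat less extreme PPoS values near the cut-offs.
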